4.3.5 Treatment Discontinuation Criteria

Tumor assessments for all subjects should continue as per protocol even if dosing is discontinued.

- Nivolumab treatment should be permanently discontinued for the following:
 - Any Grade 2 drug-related uveitis, eye pain or blurred vision that does not respond to topical therapy and does not improve to Grade 1 severity within the retreatment period OR requires systemic treatment
 - Any Grade 3 non-skin, drug-related adverse event lasting > 7 days, with the following exceptions:
 - ◆ Grade 3 drug-related uveitis, pneumonitis, bronchospasm, hypersensitivity reaction, or infusion reaction of any duration requires discontinuation
 - ◆ Grade 3 drug-related endocrinopathies, adequately controlled with only physiologic hormone replacement do not require discontinuation. Adrenal insufficiency requires discontinuation regardless of control with hormone replacement.
 - ◆ Grade 3 drug-related laboratory abnormalities do not require treatment discontinuation except:
 - Grade 3 drug-related thrombocytopenia > 7 days or associated with bleeding requires discontinuation
 - Grade ≥ 3 drug-related AST, ALT or total bilirubin requires discontinuation*
 - Concurrent AST or ALT > 3x ULN and total bilirubin > 2x ULN

* In most cases of Grade 3 AST or ALT elevation, study treatment will be permanently discontinued. If the investigator determines a possible favorable benefit/risk ratio that warrants

continuation of study treatment, a discussion between the investigator and the BMS Medical Monitor/designee must occur.

- Any Grade 4 drug-related adverse event or laboratory abnormality, except for the following events:
 - ◆ Grade 4 neutropenia \leq 7 days does not require discontinuation
 - ◆ Grade 4 lymphopenia or leukopenia does not require discontinuation
 - ◆ Isolated Grade 4 electrolyte imbalances/abnormalities that are not associated with clinical sequelae and are corrected with supplementation/appropriate management within 72 hours of their onset do not require discontinuation
 - ◆ Isolated Grade 4 amylase or lipase abnormalities those are not associated with symptoms or clinical manifestations of pancreatitis. The Sponsor Medical Monitor designee should be consulted for Grade 4 amylase or lipase abnormalities.
- Any dosing interruption lasting $>$ 6 weeks with the following exceptions:
 - ◆ Dosing interruptions to manage drug-related adverse events, such as prolonged steroid tapers, are allowed. Prior to re-initiating treatment in a subject with a dosing interruption lasting $>$ 6 weeks, the Sponsor Medical Monitor designee must be consulted. Tumor assessments should continue as per protocol even if dosing is interrupted.
 - ◆ Dosing interruptions $>$ 6 weeks that occur for non-drug-related reasons may be allowed if approved by the Sponsor Medical Monitor designee. Prior to re-initiating treatment in a subject with a dosing interruption lasting $>$ 6 weeks, the Sponsor Medical Monitor designee must be consulted. Tumor assessments should continue as per protocol even if dosing is interrupted.
- Any adverse event, laboratory abnormality, or intercurrent illness which, in the judgment of the Investigator, presents a substantial clinical risk to the subject with continued nivolumab dosing

4.3.6 Treatment of Nivolumab-Related Infusion Reactions

Since nivolumab contains only human immunoglobulin protein sequences, it is unlikely to be immunogenic and induce infusion or hypersensitivity reactions. However, if such a reaction were to occur, it might manifest with fever, chills, rigors, headache, rash, pruritus, arthralgias, hypotension, hypertension, bronchospasm, or other allergic-like reactions. All Grade 3 or 4 infusion reactions should be reported within 24 hours to the study medical monitor and reported as an SAE if it meets the criteria. Infusion reactions should be graded according to NCI CTCAE (Version 4.0) guidelines.

Treatment recommendations are provided below and may be modified based on local treatment standards and guidelines, as appropriate:

For Grade 1 symptoms: (Mild reaction; infusion interruption not indicated; intervention not indicated).

- Remain at bedside and monitor subject until recovery from symptoms. The following prophylactic premedications are recommended for future infusions: diphenhydramine 50 mg (or equivalent) and/or acetaminophen/paracetamol 325 to 1000 mg at least 30 minutes before additional nivolumab administrations.

For Grade 2 symptoms: (Moderate reaction requires therapy or infusion interruption but responds promptly to symptomatic treatment [eg, antihistamines, non-steroidal anti-inflammatory drugs, narcotics, corticosteroids, bronchodilators, IV fluids]; prophylactic medications indicated for ≤ 24 hours).

- Stop the nivolumab infusion, begin an IV infusion of normal saline, and treat the subject with diphenhydramine 50 mg IV (or equivalent) and/or acetaminophen/paracetamol 325 to 1000 mg; remain at bedside and monitor subject until resolution of symptoms. Corticosteroid and/or bronchodilator therapy may also be administered as appropriate. If the infusion is interrupted, then restart the infusion at 50% of the original infusion rate when symptoms resolve; if no further complications ensue after 30 minutes, the rate may be increased to 100% of the original infusion rate. Monitor subject closely. If symptoms recur, then no further nivolumab will be administered at that visit.
- For future infusions, the following prophylactic premedications are recommended: diphenhydramine 50 mg (or equivalent) and/or acetaminophen/paracetamol 325 to 1000 mg should be administered at least 30 minutes before nivolumab infusions. If necessary, corticosteroids (up to 25 mg of SoluCortef or equivalent) may be used.

For Grade 3 or 4 symptoms: (Severe reaction, Grade 3: prolonged [ie, not rapidly responsive to symptomatic medication and/or brief interruption of infusion]; recurrence of symptoms following initial improvement; hospitalization indicated for other clinical sequelae [eg, renal impairment, pulmonary infiltrates]. Grade 4: Life-threatening; pressor or ventilatory support indicated).

- Immediately discontinue infusion of nivolumab. Begin an IV infusion of normal saline and treat the subject as follows: Recommend bronchodilators, epinephrine 0.2 to 1 mg of a 1:1000 solution for subcutaneous administration or 0.1 to 0.25 mg of a 1:10,000 solution injected slowly for IV administration, and/or diphenhydramine 50 mg IV with methylprednisolone 100 mg IV (or equivalent), as needed. Subject should be monitored until the Investigator is comfortable that the symptoms will not recur. Nivolumab will be permanently discontinued. Investigators should follow their institutional guidelines for the treatment of anaphylaxis. Remain at bedside and monitor subject until recovery of the symptoms.

In case of late-occurring hypersensitivity symptoms (eg, appearance of a localized or generalized pruritus within 1 week after treatment), symptomatic treatment may be given (eg, oral antihistamine or corticosteroids).

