The study will close after the last enrolled subject completes 5 year follow up. The duration of the study will be 6.5 years.

Study Population: Patients with Stage 3b/4 NSCLC (squamous or non-squamous histology) who have experienced disease progression or recurrence during or after at least one systemic therapy for advanced or metastatic disease. Subjects must meet all eligibility criteria specified in [Section 3.3](#) of the protocol.

Study Assessments: Main assessments include: Incidence, severity and outcome of select adverse events, and specific related laboratory abnormalities. Exploratory assessments include incidence and severity of all adverse events, laboratory abnormalities, efficacy measures, patient reported outcomes [REDACTED].

Statistical Considerations:

Sample Size: In order to further characterize the frequency and outcome of the rather infrequent treatment related select adverse of high grade (Grade 3-5), the current study will treat approximately 780 subjects with nivolumab. This sample size will allow for estimating an incidence rate of 0.5% (n=4 subjects with events) with a 95% CI (confidence interval) of (0.14%, 1.31%), or an incidence rate of 2% (n=16 subjects with events) with a 95% CI of (1.18%, 3.31%).

This study also includes a randomization step reserved to subjects who received nivolumab for 1 year (52 weeks). In MDX1106-03, 27% of NSCLC subjects (10 of 37) were still on treatment [95% CI of (12.7%, 41.3%)] at Week 48. In the present study any subjects (all subgroups included) who are still benefiting from therapy after 52 weeks (estimated to be between 99 and 322 subjects) will be randomized in order to continue treatment without any change in Cohort A, or to discontinue treatment in Cohort B, respectively.

Endpoints: The primary objective of the study will be assessed by measuring the incidence for high grade (Grade 3-4 and Grade 5) treatment related select adverse events.

The select adverse events of interest are the following: pneumonitis, interstitial nephritis, diarrhea/colitis, hepatitis, rash, endocrinopathies, and hypersensitivity/infusion reaction events.

The secondary objective of the study will be assessed by measuring the following:

- incidence for high grade (Grade 3-4 and Grade 5) select adverse events
- median time to onset, median time to resolution (Grade 3-4) of the select adverse events

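### Section 4.3.6 gives no single rule for infusion-reaction symptoms that recur after restart: the Grade 2 text withholds drug for that visit only, while the Grade 3 text and Section 4.3.5 stop it permanently

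*Combined protocol and SAP*

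**What the plan says.** Section 4.3.6 of the protocol sets out infusion-reaction management by grade.

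- **Grade 2 text.** After an interruption, the site is to "restart the infusion at 50% of the original infusion rate when symptoms resolve". On recurrence: "If symptoms recur, then no further nivolumab will be administered at that visit". The next bullet, under the same Grade 2 heading, begins "For future infusions, the following prophylactic premedications are recommended".
- **Grade 3 or 4 text.** The Grade 3 description includes "recurrence of symptoms following initial improvement; hospitalization indicated for other clinical sequelae". The instruction is "Nivolumab will be permanently discontinued".
- **Section 4.3.5** lists, among the criteria for permanent discontinuation, "Grade 3 drug-related uveitis, pneumonitis, bronchospasm, hypersensitivity reaction, or infusion reaction of any duration requires discontinuation".

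Three other provisions bear on how these are read. Section 4.3.6 says that reactions are graded by CTCAE v4.0, that Grade 3 or 4 reactions go to the medical monitor within 24 hours, and that its treatment text consists of recommendations that sites may adapt to local practice. Section 4.3.5 has no such qualifier for infusion reactions. The Synopsis includes "endocrinopathies, and hypersensitivity/infusion reaction events" among the select adverse events, and Sections 8.3.1 and 8.4.2 count only treatment-related select events of Grade 3-4 and Grade 5, tabulated by worst CTCAE v4.0 grade.

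**The concern.** A site facing a recurrence on restart is probably already working in the Grade 2 text, because that is where the restart instruction sits. That text tells it what to do next and then moves on to later dosing. Nothing there points to the Grade 3 description a few lines below, which covers the same event and ends in permanent discontinuation.

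Three things are at stake:

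- **Subject safety.** Whether the subject may be dosed again depends on which text the site applies.
- **Reporting.** The 24-hour notice to the medical monitor is tied to Grade 3 or 4. An event left at Grade 2 would not trigger it, although a reaction meeting the seriousness criteria would still be reported under Section 6.1.1.
- **Consistency of grading.** The trial exists to measure uncommon high-grade select events. Section 1.1.7 adds that Amendment 04 will assess a 30-minute infusion, for which infusion reactions are directly relevant.

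**Working it through.** **Step 1: follow one event through the texts.**

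1. A reaction leads to interruption. Restart is conditional on symptoms having resolved (Section 4.3.6, Grade 2).
2. Symptoms recur after restart. By step 1 this recurrence follows improvement.
3. Under the Grade 2 text, drug is withheld for that visit. The bullet on later infusions does not exclude subjects who recurred. Sections 4.3.1.1 and 4.3.3 treat a Grade 2 non-skin drug-related event as a reason to delay and later resume.
4. Under the Grade 3 description the same recurrence is a listed feature. Section 4.3.6 then requires a permanent stop, and so does Section 4.3.5, at any duration.
5. No sentence links the two texts or ranks them.

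**Step 2: when does the primary numerator change?** Grade is set by CTCAE v4.0 (Sections 4.3.6 and 8.4.2). The only text in Section 4.3.6 that attaches a grade to recurrence after improvement attaches Grade 3. An event is therefore lost from the numerator only if a site leaves it at Grade 2 because the recurrence step stands under that heading.

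**Step 3: the plan's own figures.** With Clopper-Pearson limits (lower = 2.5% quantile of Beta(x, n-x+1), upper = 97.5% quantile of Beta(x+1, n-x)), 4/780 gives 0.14% to 1.31% and 16/780 gives 1.18% to 3.31%. All 16 rows of Table 8.1-1 reproduce. No stated figure is wrong.

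**Step 4: can the effect be sized?** Inputs:

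- Table 1.1-1 (Phase 1 study): 15/306 infusion reactions of any grade and 2/306 of Grade 3-4. Below Grade 3: 15 - 2 = 13, and 13/306 = 4.2%. Over 1280 subjects: 0.0425 x 1280 = about 54.
- This 54 is a ceiling. It includes Grade 1 reactions, for which Section 4.3.6 says interruption is not indicated, so they have no restart step. The table does not separate Grade 1 from Grade 2.
- Planning rates in NSCLC (Section 1.1): 1% for infusion reactions (13/1280) and 5% for any select category (64/1280).
- The share that recurs on restart is not in the documents. It is varied here from 0 to 25% purely as an assumption.

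| Assumed share of the 54 | Added events | Infusion-reaction category | Any select category |
|---|---|---|---|
| 0% | 0 | 13/1280 = 1.02% (0.54 to 1.73) | 64/1280 = 5.00% (3.87 to 6.34) |
| 10% | 5 | 18/1280 = 1.41% (0.84 to 2.21) | 69/1280 = 5.39% (4.22 to 6.77) |
| 25% | 14 | 27/1280 = 2.11% (1.39 to 3.05) | 78/1280 = 6.09% (4.85 to 7.55) |

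Each row compares every site counting these events with no site counting them. It assumes that the planning rates contain no recurrences and that the added subjects have no other high-grade select event. With the ceiling base as well, the rows overstate any realistic effect. Even so, the any-category rate stays inside the interval around its 5% starting value.

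**The case against.** The strongest case for leaving the text alone has four parts.

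- **CTCAE already settles the grade.** The Grade 2 bullet never says that a recurrence stays Grade 2, and the Grade 3 description names it. This stands as regards the endpoint. A reader might infer that the protocol has two competing grading rules, so that the event moves in or out of the primary endpoint by design. The documents do not support that; they leave room for misgrading. The objection does not remove the management conflict: if every such recurrence is Grade 3, the Grade 2 recurrence step has no event to apply to, yet it remains an instruction.
- **A sequential reading is available.** Withholding drug at that visit is compatible with a permanent stop decided afterwards, and the bullet on later infusions covers Grade 2 reactions in general. This partly stands, and calling the two rules flatly opposite would be too strong. But the sequence is written nowhere, and a limit to one visit followed by advice on later dosing points the other way.
- **The treatment text is only advisory.** True of Section 4.3.6. The discontinuation criterion in Section 4.3.5 carries no such label, so the difference in status adds to the uncertainty.
- **The effect is unquantified.** This stands. A reader might infer from the table above that the infusion-reaction rate could double. That needs an assumed recurrence share, a base that includes Grade 1 reactions, and uniform undergrading. In Table 1.1-1 the specific term infusion-related reaction had 0 of 12 events at Grade 3-4; the two Grade 3-4 events in the category were hypersensitivity.

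**Conclusion.** The inconsistency is real and wrong as written: one event satisfies two texts that differ on whether the subject may be dosed again, with no rule of precedence. This rests on wording alone, and on reading the Grade 3 list as alternatives, since its items are separated by semicolons with no connecting word.

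The main consequences are uneven handling of the same reaction across sites and a possible missed 24-hour report. The consequence for the primary endpoint is conditional on a site keeping the event at Grade 2 against the stated grading standard. Its size cannot be estimated from the documents. It is probably small for the overall rate and would show, if anywhere, in the infusion-reaction category, where about 1% is expected. The sample-size figures are unaffected. The text should be corrected, but the point does not call the primary analysis into question.

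**What to change.** Reconcile the Grade 2 and Grade 3 texts of Section 4.3.6 with each other and with Section 4.3.5. State once which grade applies when symptoms recur after restart, and make the management and 24-hour reporting instructions follow from that grade. Tell sites, so that the same grading feeds the primary table. Which rule is right is for the sponsor's clinical team; none is proposed here.

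The cost is a wording change in one section, with a matching check of Section 4.3.5, and a site notice. No visits, subjects or new analyses are needed. A derived flag for restart and recurrence, with a sensitivity line, might look attractive because Table 5.1-2 records infusion start and stop times. Those times do not show whether symptoms resolved or returned, so the flag could not be built from them and is not recommended.

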4.4 Blinding/Unblinding

Not applicable.

4.5 Treatment Compliance

Treatment compliance will be monitored by drug accountability as well as the subject's medical record and eCRF.

4.6 Destruction and Return of Study Drug

4.6.1 Destruction of Study Drug

For this study, study drugs (those supplied by BMS or sourced by the investigator) such as partially used study drug containers, vials and syringes may be destroyed on site.

Any unused study drugs can only be destroyed after being inspected and reconciled by the responsible BMS Study Monitor unless study drug containers must be immediately destroyed as required for safety, or to meet local regulations (eg, cytotoxics or biologics).

On-site destruction is allowed provided the following minimal standards are met:

- On-site disposal practices must not expose humans to risks from the drug.
- On-site disposal practices and procedures are in agreement with applicable laws and regulations, including any special requirements for controlled or hazardous substances.
- Written procedures for on-site disposal are available and followed. The procedures must be filed with the site's SOPs and a copy provided to BMS upon request.
- Records are maintained that allow for traceability of each container, including the date disposed of, quantity disposed, and identification of the person disposing the containers. The method of disposal, ie, incinerator, licensed sanitary landfill, or licensed waste disposal vendor must be documented.
- Accountability and disposal records are complete, up-to-date, and available for the Monitor to review throughout the clinical trial period.

If conditions for destruction cannot be met the responsible BMS Study Monitor will make arrangements for return of study drug.

It is the investigator's responsibility to arrange for disposal of all empty containers, provided that procedures for proper disposal have been established according to applicable federal, state, local, and institutional guidelines and procedures, and provided that appropriate records of disposal are kept.

4.6.2 Return of Study Drug

If study drug will not be destroyed upon completion or termination of the study, all unused and/or partially used study drug that was supplied by BMS must be returned to BMS. The return of study drug will be arranged by the responsible BMS Study Monitor.

It is the investigator's responsibility to arrange for disposal of all empty containers, provided that procedures for proper disposal have been established according to applicable federal, state, local, and institutional guidelines and procedures, and provided that appropriate records of disposal are kept.

5 STUDY ASSESSMENTS AND PROCEDURES

5.1 Flow Chart/Time and Events Schedule

Table 5.1-1: Screening Procedural Outline (CA209153)

Procedure	Screening Visit (28 days prior to dosing unless otherwise specified)	Notes
Eligibility Assessments		
Informed Consent	X	
IVRS	X	An IVRS will be used to assign subject numbers, staggered enrollment of subject subgroups, and randomization at 1 year (52 weeks, \pm 2 weeks)
Inclusion/Exclusion Criteria	X	
Medical History	X	Medical history will include smoking history. In addition, mutational status of EGFR, ALK, ROS, MET, KRAS and BRAF should be collected, if available. If mutational status is not available in the medical history of subjects with non-squamous histology, EGFR and ALK mutational status must be determined as specified in Section 3.3.1 .
Safety Assessments		
Physical measurements (including performance status)	X	Includes height, weight, performance status (ECOG); baseline EKG, and a focused physical exam is to be performed at screening. C1D1 weight is to be used as baseline weight.
Vital Signs and oxygen saturation	X	Temperature, BP, HR, RR, O ₂ saturation by pulse oximetry at rest (also monitor amount of supplemental oxygen if applicable). Obtain vital signs at screening visit and within 72 hours of first dose
Assessment of Signs and Symptoms	X	After obtaining Informed Consent, assess all signs and symptoms within 14 days of first dose, prior to study treatment initiation
Concomitant medications	X	Within 14 days of first dose
Laboratory Tests	X	Labs performed locally within 14 days prior to first dose (unless otherwise specified): CBC with differential, serum chemistry (BUN or serum urea level, serum creatinine, sodium, potassium, calcium, magnesium, phosphate, chloride, and glucose), liver function tests (AST, ALT, total bilirubin, alkaline phosphatase, albumin, LDH). The following labs can be performed locally within 28 days prior to first dose: TSH, free T3, free T4, hepatitis B surface antigen (HBV sAg) and Hepatitis C

Table 5.1-1: Screening Procedural Outline (CA209153)

Procedure	Screening Visit (28 days prior to dosing unless otherwise specified)	Notes
		antibody (HCV Ab) or Hepatitis C RNA (HCV RNA)
Pregnancy Test	X	Within 24 hours prior to first dose for WOCBP only (serum or urine at the site).
Radiographic Tumor Assessment (Chest, Abdomen, Head)	X	Within 28 days prior to first dose. CT/MRI of brain (with contrast, unless contraindicated) required for subjects who have known history of brain metastases or if clinically indicated.. Additional sites of known or suspected disease (including pelvis) should be imaged at the screening visit.
Archived Tumor Tissue or Recent Tumor Biopsy	X	
One formalin-fixed paraffin embedded tumor tissue block, or 10 minimum FFPE unstained slides are to be submitted if available. Submit a copy of the original pathology report along with the sample. Tissue samples from different biopsy procedures are to be submitted if available with each matching pathology report and biopsy date.
 
NOTE: For subjects previously enrolled in CA 209118, tumor tissue and/or laboratory data generated from tissue collected in CA209118 is to be utilized for this study.

Table 5.1-2: On-Study Procedural Outline (CA209153)

Procedure	C1D1 (Cycle 1 Day 1)	Each Cycle (Every 2 weeks) on Day 1	Every 3 Cycles (Every 6 weeks) on Day 1	Every 4 Cycles (Every 8 weeks) on Day 1	Notes
Safety Assessments					
Vital Signs and oxygen saturation ^a	X	X			Within 72 hours prior to dosing. Include temperature, blood pressure, heart rate, respiratory rate, oxygen saturation by pulse oximetry at rest prior to dosing and at any time there are new or worsening respiratory symptoms. (see Section 5.3.2) Patients randomized to Cohort B will be assessed every 2 or 4 weeks for clinical assessment and physical examination per investigator decision. If nivolumab is restarted, every two week assessment schedule must be resumed.
Adverse Events Assessment			Continuously		Continuously assessed using NCI CTCAE v. 4.0.
Physical measurements and target physical exam (including Performance Status)	X	X			Includes weight, ECOG status, and targeted physical exam as clinically indicated Patients randomized to Cohort B will be assessed every 2 or 4 weeks for clinical assessment and physical examination per investigator decision. If nivolumab is restarted, every two week assessment schedule must be resumed.
Laboratory Tests^b					Cohort B: For subjects randomized to Cohort B, lab tests will be performed every 4 weeks. If nivolumab is restarted, every two week lab assessment schedule must be resumed.

Table 5.1-2: On-Study Procedural Outline (CA209153)

Procedure	C1D1 (Cycle 1 Day 1)	Each Cycle (Every 2 weeks) on Day 1	Every 3 Cycles (Every 6 weeks) on Day 1	Every 4 Cycles (Every 8 weeks) on Day 1	Notes
Complete blood counts (CBC) (Obtain results prior to dosing on infusion days)	X	X			Screening labs performed within 14 days of C1D1 visit do not need to be repeated unless clinically indicated. For C2D1 and beyond, to be performed within 72 hours prior to dosing. Tests include WBC count with differential, lymphocyte count, ANC, hemoglobin, hematocrit, and platelet count
Serum chemistry (Review results prior to dosing on infusion days)	X	X			Screening labs performed within 14 days of C1D1 visit do not need to be repeated unless clinically indicated. For C2D1 and beyond, to be performed within 72 hours prior to dosing. BUN or serum urea level, serum creatinine, sodium, potassium, calcium, magnesium, phosphate, chloride, glucose, and LDH
Liver function (Review results prior to dosing on infusion days)	X	X			Screening labs performed within 14 days of C1D1 visit do not need to be repeated unless clinically indicated. For C2D1 and beyond, to be performed within 72 hours prior to dosing. Aspartate aminotransferase (AST), alanine aminotransferase (ALT), total bilirubin, alkaline phosphatase, albumin
Thyroid function	X		X*		Screening labs performed within 28 days of C1D1 visit unless clinically indicated. TSH (reflex to free T3 and free T4 if abnormal result) Thyroid function test may be performed within 72 hours prior to dosing. *Cohort B: TSH/thyroid function tests can be done every 12 weeks.

Table 5.1-2: On-Study Procedural Outline (CA209153)

Procedure	C1D1 (Cycle 1 Day 1)	Each Cycle (Every 2 weeks) on Day 1	Every 3 Cycles (Every 6 weeks) on Day 1	Every 4 Cycles (Every 8 weeks) on Day 1	Notes
Pregnancy Test	X		X		Serum or urine test for WOCBP only, to be performed C1D1 and every 6 weeks, or more frequently as required by local standards. Serum or urine test may be performed within 24 hours of scheduled dose.
Review of concomitant medications	X	X			At each visit
Efficacy Assessments					
Radiographic tumor assessments				X	
At Week #9 (the 9th week on study with C1D1 week counted as week #1) \pm 5 days and every 8 weeks (\pm 5 days) thereafter up to 24 months from first dose then every 12 weeks (\pm 5 days) regardless of dosing schedule, until documented disease progression or discontinuation of study therapy in subjects receiving nivolumab beyond progression.
 
Assessments should include all areas that are being monitored and new areas if clinically indicated (with contrast unless contraindicated). Follow RECIST 1.1 criteria.
 
Subjects with a history of brain metastasis (BM) should have surveillance MRI approximately every 12 weeks, or sooner if clinically indicated.
 
After 24 months of treatment, the frequency of surveillance brain MRI or CT scans will be every 6 months or earlier, if clinically indicated, for subjects with known brain metastases.

Table 5.1-2: On-Study Procedural Outline (CA209153)

Procedure	C1D1 (Cycle 1 Day 1)	Each Cycle (Every 2 weeks) on Day 1	Every 3 Cycles (Every 6 weeks) on Day 1	Every 4 Cycles (Every 8 weeks) on Day 1	Notes
Randomization		At 1 year (52 weeks)			Subjects that are still on study and benefiting from treatment will be randomized 1:1 to Cohort A or B.

Table 5.1-2: On-Study Procedural Outline (CA209153)

Procedure	C1D1 (Cycle 1 Day 1)	Each Cycle (Every 2 weeks) on Day 1	Every 3 Cycles (Every 6 weeks) on Day 1	Every 4 Cycles (Every 8 weeks) on Day 1	Notes
Administration of nivolumab (BMS-936558) 3 mg/kg	X	X			
All subjects start treatment on C1D1 and continue treatment every 2 weeks until disease progression, unacceptable toxicity, or withdrawal of informed consent. At 1 year (52 weeks) all subjects that remain on treatment will be randomized to Arm A or Arm B.
 
Cohort A subjects will continue treated until disease progression, unacceptable toxicity, or withdrawal of informed consent.
 
Cohort B subjects will discontinue treatment at 1 year (52 weeks \pm 2 weeks). Upon progression, subjects can be retreated until progression, unacceptable toxicity, or withdrawal of informed consent.
 
Treatment for all subjects can continue beyond initial investigator-assessed progression as specified in Section 4.3.4. Drug administration is $+/-$ 3 days but no less than 12 days from previous dose. Study drug infusion start and stop times will be recorded. .

LCSS and EQ-5D	X		X		
Complete every 3 cycles (every 6 weeks) on Day 1 during first 1 year (52 weeks) of treatment. After randomization at one year (52 weeks), every other cycle on Day 1.
 
Complete assessments prior to any contact with study staff if possible

^a Monitor amount of supplemental oxygen if applicable. If a subject shows changes in oxygen saturation or supplemental oxygen requirement, or other pulmonary-related signs (eg, hypoxia, fever) or symptoms (eg, dyspnea, cough) consistent with possible pulmonary adverse events, immediately evaluate to rule out pulmonary toxicity, according to the suspected pulmonary toxicity management algorithm provided in the Investigators' Brochure.

^b Review serum chemistry and liver function prior to dosing. Perform CBCs prior to dosing but results need not be reviewed prior to dosing.

Table 5.1-3: Follow-up Procedural Outline (CA209153)

Procedure	Initial Follow-Up Phase (100 days from the date of last study treatment) Follow-up Visit 1 (X01) and Visit 2 (X02)	Further Follow-up Phase (beyond X02)	Notes 
 • Subjects who discontinue treatment prior to randomization and subjects in Cohort A: Follow-up Visit 1 (X01) is to occur 30 days (\pm 5 days) after last dose or coinciding with the date of discontinuation (\pm 5 days) if date of discontinuation is greater than 35 days after last dose. • Subjects in Cohort B: Follow-up Visit 1 (X01 is to occur 30 days (\pm 5 days) after disease progression and a decision has been made to not retreat the subject or at 30 days (\pm 5 days) of discontinuation after retreatment • Follow up Visit 2 (X02) is to occur approximately 70 days (\pm 5 days) after X01
Radiographic Tumor Assessment	X	X	For subjects who discontinue study treatment for reasons other than PD, follow up scans (or MRIs when appropriate) should be performed every 8 weeks (\pm 5 days) up to 24 months from first dose then every 12 weeks (\pm 5 days) until PD, death, lost to follow-up, or withdrawal of consent; radiographic assessments should not delayed until the X01 or X02. After 24 months of treatment, the frequency of surveillance brain MRI or CT scans will be every 6 months or earlier, if clinically indicated for subjects with known brain metastases.
Safety Assessments			
Vital Signs	X		
Physical measurements	X		Includes performance status (ECOG)
Adverse Events Assessment	X	X	*Beyond 100 days from the last dose of study therapy, subjects will be followed for ongoing drug-related AEs until resolved, return to baseline or deemed irreversible, or until lost to follow-up or withdrawal of study consent.

Table 5.1-3: Follow-up Procedural Outline (CA209153)

Procedure	Initial Follow-Up Phase (100 days from the date of last study treatment) Follow-up Visit 1 (X01) and Visit 2 (X02)	Further Follow-up Phase (beyond X02)	Notes 
 • Subjects who discontinue treatment prior to randomization and subjects in Cohort A: Follow-up Visit 1 (X01) is to occur 30 days (\pm 5 days) after last dose or coinciding with the date of discontinuation (\pm 5 days) if date of discontinuation is greater than 35 days after last dose. • Subjects in Cohort B: Follow-up Visit 1 (X01) is to occur 30 days (\pm 5 days) after disease progression and a decision has been made to not retreat the subject or at 30 days (\pm 5 days) of discontinuation after retreatment • Follow up Visit 2 (X02) is to occur approximately 70 days (\pm 5 days) after X01
Laboratory Tests	X		CBC with differential, serum chemistry (BUN or serum urea level, serum creatinine, albumin, sodium, potassium, calcium, magnesium, phosphate, chloride, glucose), liver function (AST, ALT, total bilirubin, alkaline phosphatase, LDH), thyroid function (TSH, reflex to free T3 and free T4 if abnormal result)
Review of concomitant medications	X		
Pregnancy testing	X		
EQ-5D	X	X	Beyond 100 days from the last dose of study therapy, the EQ-5D will be administered every 3 months for the first 12 months, then every 6 months thereafter, as permitted by local IRB
Collection of Survival Information	X	X	Every 3 months until death, lost to follow-up, or withdrawal of study consent for 5 years following start of therapy. May be performed by phone contact or office visit.

